15.6.15.6. Other Immunosuppressant Agents

Arms A, B, and C

- Starting any new immunosuppressant agent after Day 1 for increased lupus disease activity will cause the participant to be declared a treatment failure. An immunosuppressant agent may however be replaced with one of the agents listed below due to documented toxicity or lack of availability. Replacement to be determined by clinical review
- New topical immunosuppressive agents (e.g., eye drops, topical creams) are allowed after Day 1.

Arms A and B

- Participants can maintain their baseline stable immunosuppressant regimen or adjust their dose as clinically required, up to the Week 4.
- At or prior to the Week 4 visit, immunosuppressants will be discontinued.
- All immunosuppressant medications post Week 4 (day after the visit 4 visit date) will be clinically reviewed to determine if they are a treatment failure.

Arms C

- Participants may continue their baseline immunosuppressant agents throughout the study.
- Dosage of existing immunosuppressant agents may be increased as clinically necessary until Week 12. From the day after the Week 12 visit, any increase in dose over the baseline (Day 1) or Week 12 visit dose, whichever is higher, will cause the participant to be declared a treatment failure.

The common allowable maximum doses for immunosuppressant agents at baseline (Day 1) and during the study (pre Week 4 for Arms A and B) are listed below:

- Azathioprine – 300 mg/day
- 6-mercaptopurine – 300 mg/day
- Mycophenolate mofetil (PO)/ mycophenolate mofetil hydrochloride (IV) – 4 g/day
- Mycophenolate sodium (PO) – 2.88 g/day
- Methotrexate – 25 mg/week
- Oral cyclophosphamide – 2.5 mg/kg/day
- Cyclosporine – 4 mg/kg/day*
- Tacrolimus – 0.2 mg/kg/day*
- Sirolimus – 2 mg/day*
- Thalidomide – 200 mg/day
- Leflunomide – 40 mg/day*
- Mizoribine – 150 mg/day
- Other immunosuppressant agents not listed above, the investigator must contact the Medical Monitor for approval

*Clinical loading dose is permitted when replacing immunosuppressant agents.

15.6.15.7. Nonsteroidal Anti-inflammatory Drugs (NSAIDs), Aspirin, and Acetaminophen

NSAIDs and aspirin should be initiated and stabilized prior to entry into the trial.

Baseline is defined as the NSAID/Aspirin received on the treatment start date (Day 1)

NSAIDs may be continued and dose adjusted as clinically indicated until 8 weeks before efficacy visits, i.e., Weeks 52, 64, and 104. During the intervals of 8 weeks before these efficacy endpoints, any increase in the NSAID dose above the dose at Day 1 or the visit day starting the interval of 8 weeks prior to these key efficacy visits, whichever is higher, will declare the participant as a treatment failure unless the NSAID is given for <7 days. The day of the Week 44, 56, and 96 visits will count as the start of these 3 intervals.

An NSAID may be replaced with another NSAID due to documented toxicity or lack of availability. Replacement due to toxicity/ lack of availability will be assessed during clinical adjudication.

New NSAIDs may not be added after Day 1 unless given for <7 days. Initiation of an NSAID after Day 1 that is given ≥ 7 days will declare the participant as a treatment failure.

NSAIDs with an administration route of ‘TOPICAL’ or ‘CONJUNCTIVAL’ will not be considered as TF’s.

Aspirin will not be considered in the NSAID TF rules.

Daily doses of aspirin up to 1000 mg/day are allowed at any time during the study. Daily doses of aspirin above 1000 mg/day may be initiated at any time up to the Week 44 visit and may continue through the end of the study. For participants who never received an aspirin regimen at a dose >1000 mg/day between the Day 1 and Week 44 visit, starting a new aspirin regimen at a dose >1000 mg/day after the Week 44 visit will declare the participant a treatment failure unless the aspirin is given for <7 days.

Daily doses of aspirin above 1000 mg/day may not be initiated in the 8 weeks before Week 64 and 104. The same rules as at Week 44 will be applied at Weeks 56 and 96

ACETYLSALICYLATE LYSINE (in mg) will be converted to standardised dose by multiplying by 0.556.

Acetaminophen (paracetamol) is primarily an analgesic and lacks the anti-inflammatory properties of other NSAIDs. The use of acetaminophen is recommended when possible to treat non-SLE related conditions, in the absence of a pre-existing hepatic function deficiency.

PRN use of NSAIDs or Aspirin will be identified as a potential TF and reviewed on a by subject review basis.

15.6.15.8. Prohibited Medications

Medications prohibited by the protocol specified rule of:

- Other investigational agents (biologic or non-biologic). Investigational applies to any drug not approved for sale in the country in which it is being used.
- Co-enrollment into another study of a different investigational agent or that may interfere with the conduct of this protocol.

cannot be assessed by the data recorded on the CRF, but would be identified through CRA monitoring. Should such events occur they will be addressed through the TF review process.

Receiving a live vaccine is prohibited due to safety reasons but is not a treatment failure criterion.

15.6.15.9. Belimumab in Year 2

This use of PI prescribed belimumab in Year 2 is a treatment failure for subjects in Arms A and B. Incorrectly taking Year 1 belimumab in Year 2 is not a treatment failure. For subjects in Arms A and B all belimumab taken in Year 2 will be adjudicated to determine if it is an incorrect late dose or a prescribed re-start medication.

Receiving belimumab is not a treatment failure for Arm C subjects.

15.6.16. Coronavirus Disease 2019 (COVID-19) Environment Onset Date

A COVID-19 environment onset date has been defined by GlaxoSmithKline for each Country as:

| Country | COVID-19) Environment Onset Date |
|--------------------|---|
| Argentina | 10/FEB/2020 |
| Brazil | 10/FEB/2020 |
| Canada | 10/MAR/2020 |
| France | 25/FEB/2020 |
| Germany | 10 FEB/2020 |
| Korea, Republic of | 10/FEB/2020 |
| Mexico | 10/FEB/2020 |
| Netherlands | 10/FEB/2020 |
| Russia Federation | 13/MAR/2020 |
| Spain | 10/FEB/2020 |
| United States | 10/FEB/2020 |

This represents the best estimate of the outbreak of COVID-19 within each Country at this time.

15.7. Appendix 7: Reporting Standards for Missing Data

15.7.1. Premature Withdrawals

| Element | Reporting Detail |
|---------|--|
| General | 
 • Subject study completion (i.e. as specified in the protocol) is defined as completing all phases of the study, including the Week 104 visit. • Withdrawn subjects will not be replaced in the study. • All available data from participants who were withdrawn from the study will be listed and all available planned data will be included in summary tables and figures, unless otherwise specified. • Withdrawal visits will be slotted as per Appendix 3 or will be summarized as withdrawal visits. |

15.7.2. Missing Data

| Element | Reporting Detail |
|----------|---|
| General | 
 • Missing data occurs when any requested data is not provided, leading to blank fields on the collection instrument: 
 ○ These data will be indicated by the use of a “blank” in subject listing displays. Unless all data for a specific visit are missing in which case the data is excluded from the table. ○ Answers such as “Not applicable” and “Not evaluable” are not considered to be missing data and should not be displayed as missing. |
| Outliers | 
 • Any participants excluded from the summaries and/or statistical analyses will be documented along with the reason for exclusion in the clinical study report. |

15.7.2.1. Missing and Partial Dates

| Element | Reporting Detail |
|---|--|
| General | 
 • Partial dates will be displayed as captured in subject listing displays. |
| Adverse Events | 
 • The eCRF allows for the possibility of partial dates (i.e., only month and year) to be recorded for AE start and end dates; that is, the day of the month may be missing. In such a case, the following conventions will be applied for calculating the time to onset and the duration of the event: 
 ○ Missing Start Day: First of the month will be used unless this is before the start date of study treatment; in this case the study treatment start date will be used and hence the event is considered On treatment as per Appendix 4: Study Phases and Treatment Emergent Adverse Events. ○ Missing Stop Day: Last day of the month will be used, unless this is after the stop date of study treatment; in this case the study treatment stop date will be used. • Completely missing start or end dates will remain missing, with no imputation applied. Consequently, time to onset and duration of such events will be missing. |
| Concomitant Medications/ Medical History | 
Missing concomitant medication start date (CMSTDT) is imputed as treatment start date (TRTSDT) unless:
 
 ○ concomitant medication end date (CMENDT) is prior to treatment start date (TRTSDT), whether CMENDT is complete (DD/MM/YY) or partial (some combination of CMENDT day, month or year imputed) OR ○ The month or month and year of the partial CMSTDT are different from the month and/or year of TRTSDT OR |

| Element | Reporting Detail |
|---------|--|
| | 
○ "Taken prior to study?" is checked. 
If any of the above conditions are met then CMSTDT is imputed with JAN for missing month and 01 for missing day, whatever is applicable. The recorded partial date will be displayed in listings.
 |

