Randomization and the first dose of belimumab should be completed within 35 days of initiation of screening procedures. Participants will be receiving stable standard therapy at entry. At randomization, participants will be stratified by their screening SLEDAI-2K score (≤9 vs. ≥10), by immunosuppressant use at screening (immunosuppressant use vs. no use) and by screening corticosteroid dose (prednisone equivalent ≤10 mg/day vs. >10 mg/day). Belimumab will be administered SC on Day 1 and then weekly (i.e., every 7 days ±1 day) through Week 51 for Arms A and B, and through Week 103 for Arm C. SC injections will be administered at alternating injection sites between the left or right thighs and the abdomen. Rituximab-placebo or rituximab will be administered by intravenous (IV) infusions at Weeks 4 and 6 for Arms A and B. Participants in Arms A and B will be administered a pre-medication regimen 30 minutes before each rituximab-placebo or rituximab infusion on Weeks 4 and 6, including methylprednisolone 100 mg IV or equivalent, an antihistamine, and acetaminophen or equivalent.

Participants in any arm who are deemed treatment failures for efficacy endpoints at any time during the study will be encouraged to remain in the study and continue to have all efficacy and safety assessments.

Participants randomized to Arms A or B who enter the study on immunosuppressants will discontinue immunosuppressants prior to or on the day of the Week 4 visit. Continuing the stable immunosuppressant dose until Week 4 allows participants to receive 3 weeks of belimumab SC prior to discontinuing their immunosuppressants. Corticosteroids may be adjusted as necessary during this transition period. If participants in Arms A and B receive immunosuppressants after the Week 4 visit they will be deemed treatment failures. Participants in Arm C will continue their stable immunosuppressants throughout the study at the discretion of the investigator. If participants in Arm C require an increased dose of their stable immunosuppressant after Week 12 or addition of a new immunosuppressant they will be considered a treatment failure.

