During the 52-week double-blind portion of the study, participants in Arms A and B who cannot tolerate discontinuation of immunosuppressants or taper of corticosteroids or, in the opinion of the investigator, require added therapy, will be considered treatment failures for the efficacy endpoints. Blinding to the treatment assignments in Arms A and B will be maintained. At the investigator's discretion, these participants may continue treatment with belimumab, and/or be treated with additional SLE therapies as necessary, including corticosteroids and/or immunosuppressants. Participants in Arm C who are unable to tolerate the corticosteroid taper or, in the opinion of the investigator, require increased doses of their baseline immunosuppressants or addition of a new immunosuppressant will be considered treatment failures for the efficacy endpoints.

Participants in Arms A and B will enter into the 52-week treatment-free, observational phase of the study after completing Week 52 (Weeks 53 through 104). "Treatment-free" refers to no active treatment with study treatment (i.e., belimumab and/or rituximab). Participants in Arm C will continue to receive belimumab SC and their stable immunosuppressants during Weeks 53 through 104. For participants in all three treatment arms, treatment with anti-malarials, NSAIDs, and/or corticosteroids with a prednisone equivalent dose of ≤5 mg/day will be allowed in Weeks 53 to 104.

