2.6. Duration of Disease Control (RAP Section 15.6.4)

The formula for the duration of disease control specified in RAP Section 15.6.4 should be as follows:

Duration of disease control = longest period where
Last visit of disease control – **First** visit of disease control + 1

Also, it is not appropriate to derive disease control at Baseline, therefore the first visit of disease control considered in this calculation will always be the first post-baseline visit where the subject meets the disease control criteria.

2.7. Lupus Low Disease Activity State (LLDAS) Missing Data (RAP Section 7.4 and Section 15.6.9)

The RAP does not explicitly state what happens when the subject has missing data for a component of their LLDAS assessment. Adding these clarifying sentences would be clearer:

“Within each criteria, a subject with an incomplete assessment (due to missing data) will be considered as missing, i.e. observed data will be presented for the individual criteria.

A subject is only considered an overall responder for LLDAS if they are a responder for all 6 criteria, i.e. missing data within one or more criteria would make them an overall non-responder.”

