5.12. On Treatment

For Year 1 on treatment is defined as from 1st dose of belimumab to the latter of: last dose of belimumab + 28 days or last dose of rituximab + 28 days

For Year 1&2 arm C, on treatment is defined as from 1st dose to last dose of belimumab + 28 days.

For Year 2 Arms A&B on treatment is not defined as there is no on treatment reporting (as all subjects are off treatment)

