| 
Clinical Remission Sustained For At Least 24 Weeks
 
Sustained response will be reported for all weeks post Week 52 (Year 2), and at any timepoint (i.e. any subjects who had a sustained response at any time during Year 2). Statistical analysis will only be conducted at Week 104 and at ‘any timepoint’.
 
A subject has a sustained remission at a visit if all of the following criteria are met:
 
 1 In clinical remission at the visit 2 In clinical remission at the first visit at least 24 study weeks prior, or if clinical remission cannot be assessed at that visit, then in clinical remission at the visit prior. 3 In clinical remission for all assessed visits between (1) and (2). – Note assessments can be missing. 
Note: 24 weeks refers to the difference in visit ‘labels’ not calendar weeks between visits.
 |

[figure not shown]
| |
|--|
| Time to Clinical Remission Sustained to Week 104 |
| The first visit of sustained clinical remission is defined as the 1 st visit that the subject is a clinical remission responder and all subsequent visits up to and including Week 104 the subjects is also a clinical remission responder. Missing assessments are not considered (the rules for sustained response for at least 24 weeks as defined above are also applied here). |
| Time to clinical remission sustained to Week 104 = 1 st visit of sustained clinical remission - treatment start date (Day 1) +1 |
| Duration of Clinical Remission |
| The duration of clinical remission is defined as the longest period between 2 visits that the subject is a clinical remission responder at all visits. Missing assessments are not considered Duration of clinical remission = longest period where 1 st visit of clinical remission – last visit of clinical remission + 1 |

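### The partial-date rule for adverse events ends post-treatment events before they begin, and the clinical-remission duration formula in SAP 15.6.5 is still reversed

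*SAP*

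**What the plan says.** **Adverse-event dates.** SAP 15.7.2.1 gives conventions "for calculating the time to onset and the duration of the event" when only month and year are recorded. A missing stop day becomes the last day of the month "unless this is after the stop date of study treatment; in this case the study treatment stop date will be used". For a missing start day the rule is "First of the month will be used unless this is before the start date of study treatment; in this case the study treatment start" date, and the event is then classed as on treatment. Neither SAP addendum amends these rules.

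**When treatment stops.** Belimumab is given weekly "through Week 51 for Arms A and B, and through Week 103 for Arm C" (Protocol Synopsis). SAP 5.12 says of the second year: "For Year 2 Arms A&B on treatment is not defined as there is no on treatment reporting (as all subjects are off treatment". SAP 8.1.1.3 nevertheless reports adverse events starting from the day after the Week 52 visit up to the Week 104 visit. SAP 8.1.2 requires the adverse-event listings to show duration and study day of resolution. The second addendum (2.1.9) keeps the Year 2 adverse-event and serious-adverse-event listings.

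**Clinical-remission duration.** SAP 15.6.5 asks for the longest period, computed as first "visit of clinical remission – last visit of clinical remission + 1". SAP 7.8.5, which names both duration endpoints, gives the opposite order: last qualifying visit minus first, plus 1. Addendum 1 Section 2.6 says "The formula for the duration of disease control specified in RAP Section 15.6.4 should be as follows" and puts the last visit first. It covers disease control only. Table 22.09, duration of clinical remission, stays in the end-of-study set.

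**The concern.** The stop rule assumes that events end while treatment is running. In Arms A and B the whole second year falls after the planned last dose, so a partial stop date there is pulled back to a date before the event started. A negative duration is at least visible. A truncated event, one that began on treatment and ran past its end, gets a positive and plausible duration that no range check would catch.

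The remission formula raises a different problem. The derivation appendix and the methods section disagree on the sign of a retained secondary endpoint, and the addendum that corrected the same slip for disease control left this one standing.

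The start rule lacks a check that the concomitant-medication rule in the same table has: whether the recorded month is the month of first dose. Without it, an event known to precede treatment can be classed as on treatment.

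**Working it through.** The documents state no figure to reproduce, so the rules were applied literally.

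**Inputs**
- Last planned belimumab dose (Protocol Synopsis): Arms A/B at Week 51, Day 51 × 7 + 1 = 358; Arm C at Week 103, Day 103 × 7 + 1 = 722.
- Target visit days (SAP 15.3.1): Week 52 = 365, Week 64 = 449, Week 104 = 729. Year 2 onsets therefore fall on about Days 366 to 729.
- Assumptions: treatment stop is the last belimumab dose, and duration counts both end days (stop - onset + 1). To place month-ends, Day 1 is set to 7 January 2019 and the event lasts 7 days; these two choices affect only the month-end values.

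**Stop rule.** Imputed stop = the earlier of month-end and treatment stop. For any onset after treatment stop T, the duration is T - onset + 1, which is zero or negative.

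| Onset, Arms A/B | Under 15.7.2.1 | Month-end without the cap |
|---|---|---|
| Day 366 | 358 - 366 + 1 = -7 | 25 |
| Day 449 | 358 - 449 + 1 = -90 | 32 |
| Day 561 | 358 - 561 + 1 = -202 | 12 |
| Day 729 | 358 - 729 + 1 = -370 | 28 |

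Every onset from Day 366 to Day 729 gives a negative value. In Arm C, onsets on Days 366, 449 and 561 keep their month-end durations (25, 32 and 12), because month-end falls before Day 722.

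Reading treatment stop as the last dose plus the 28 days used in SAP 5.12 (Day 386) shifts the boundary but does not remove the fault: an onset on Day 729 still gives 386 - 729 + 1 = -342.

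**Truncation.** An event from Day 340 to Day 420 lasts 420 - 340 + 1 = 81 days. The rule gives 358 - 340 + 1 = 19. Month-end gives 111 under the same calendar: an overestimate, but one limited to the days left in the recorded month.

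**Clinical remission**

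| First to last visit | 15.6.5 (first - last + 1) | 7.8.5 (last - first + 1) |
|---|---|---|
| Week 52 to 64 | 365 - 449 + 1 = -83 | 85 |
| Week 64 to 104 | 449 - 729 + 1 = -279 | 281 |
| Week 52 to 104 | 365 - 729 + 1 = -363 | 365 |
| One visit only | 1 | 1 |

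Because 15.6.5 takes the longest such period, a literal maximum favours the shortest spell. A participant with one isolated remission visit and a later spell from Week 52 to Week 104 would score 1 (the larger of 1 and -363), not 365.

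**Start rule.** This is a comparison of texts. The concomitant-medication row does not impute the first-dose date when the recorded month or year differs from that of first dose. The adverse-event row has no such condition. Screening can last 35 days (Protocol 9.1), so an onset in the month before first dose is possible.

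**The case against.** The case for leaving this alone is substantial in parts.

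- **Reach of the stop rule.** It applies only to dates recorded as month and year. SAP 15.7.2.1 displays partial dates as captured, so the recorded month stays visible. Incidence, Year 1/Year 2 attribution and exposure-adjusted rates use onset or time to first event. This stands. A reader might infer that Year 2 safety reporting is wrong for all 210 of 280 planned participants in Arms A and B. The documents do not support that: 210 is the number exposed to the rule, and no frequency of partial stop dates is given.
- **Re-start belimumab.** SAP 15.7.2.1 does not say whether re-start dosing moves the treatment stop date; SAP 6.6 excludes it from the discontinuation derivation. The negative durations are therefore claimed only for participants off belimumab.
- **Remission formula.** SAP 7.8.5 already has the right order, and a negative longest period contradicts the definition printed just before the formula in 15.6.5. A programmer might well correct it unprompted. It would be too strong to say that the plan's only formula is wrong, or that Table 22.09 will show negative durations. But 7.8.5 was equally right for disease control, and the sponsor still issued a correction there.
- **Start rule.** Protocol 9.7.1 sends most occurrences between consent and first dose to medical history; the exception is serious events related to study participation or a sponsor product. A reader might infer wide contamination of treatment-emergent counts, but only a few events could qualify. SAP 8.1.2 does plan a pre-treatment adverse-event table, so the category need not be empty.

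**Conclusion.** The concern holds in a limited form.

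1. The stop rule gives wrong values as written. For Arms A/B participants off belimumab in Year 2 it yields durations of -7 to -370 days for onsets on Days 366 to 729. In any arm it shortens events that continue past treatment stop. The consequence is confined to derived duration and resolution day in the adverse-event listings, and in the serious-event listing if it carries those columns. This rests on treatment stop meaning the last belimumab dose. How many rows are affected cannot be known from the documents.
2. SAP 15.6.5 and 7.8.5 contradict each other on clinical-remission duration and must be reconciled. The endpoint lies outside the testing hierarchy.
3. The start-rule gap is minor. It is the only one of the three that could alter an adverse-event count, and only by a few events.

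No primary or major secondary analysis is touched. The reason to act is that the rules are plainly wrong and cheap to correct.

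**What to change.** - **Stop day (15.7.2.1):** impute the last day of the recorded month, bounded only by death or the last contact/data cut-off date, and never earlier than onset. Remove the treatment-stop cap, and do not replace it with a study-exit cap. Protocol 9.7.3 follows serious events and events of special interest until they resolve or stabilise, so a study-exit cap would truncate them. SAP 8.1.1.4 reports events that start after the on-study period, and such a cap combined with the onset floor would collapse their partial stop dates to the onset day.
- **Clinical remission (15.6.5):** extend Addendum 1 Section 2.6 to this section, so that duration is last visit - first visit + 1, as in 7.8.5.
- **Start day (15.7.2.1):** impute the first-dose date only when the recorded month and year equal those of first dose; otherwise use the first of the recorded month.

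The cost is three lines of SAP text and the matching program changes. No new data are needed.
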